#### **4 CHANGES IN THE PLANNED ANALYSIS OF THE STUDY**

No changes made in the planned analysis of the study mentioned in the protocol version 5.0, dated 01 August 2018.

## **5 OUTCOMES**

### **5.1 PRIMARY OUTCOMES**

- Incidence of all ADRs in nintedanib treated patients
- Incidence of all SAEs in nintedanib treated patients

[figure not shown]
### **5.2 SECONDARY OUTCOMES**

[figure not shown]
#### **5.2.1 Key secondary outcome**

[figure not shown]
This section is not applicable as no key secondary outcome has specified in the protocol.

[figure not shown]
#### **5.2.2 Secondary outcome**

[figure not shown]
- Percentage of patients who require dose reductions, interruptions and discontinuation due to adverse events.

## **6 GENERAL ANALYSIS DEFINITIONS**

### **6.1 TREATMENT**

This active surveillance will include 200 IPF patients treated with nintedanib per the Indian label. They are classified into following groups:

Group B:	Patients who started treatment with nintedanib after 23rd January, 2017 and are continuing the drug at the time of participation in the active surveillance.
Group C:	Patients who have been newly prescribed nintedanib at the time of participation in the active surveillance.

In addition 200 IPF patients treated with pirfenidone will also be enrolled. They are classified into following groups:

Group II:	Patients who started treatment with pirfenidone after the 23rd January, 2017 and are continuing the drug at the time of participation in the active surveillance.
Group III:	Patients who have been newly prescribed pirfenidone at the time of participation in the active surveillance.

The medical records at the selected sites will be screened to enroll Group B patients in a retrospective manner till the date of start of their participation in this active surveillance program and prospectively thereafter. Group C patients will be enrolled prospectively. The first patient enrolled at a given site should be in the nintedanib group. Once a patient is enrolled into the nintedanib group, the site team is suggested to enroll the next eligible patient, who has initiated or will be initiating pirfenidone at the same site in the pirfenidone group.

As this is an active surveillance of patients prescribed nintedanib in the real world, no specific treatment is mandated or withheld from the patients. The choice of maintenance treatment for IPF must be according to regular medical practice and at the discretion of the physician. As for any active surveillance study, the assignment of the patient to nintedanib

or any other treatment falls within current practice and prior to the decision to talk to the patient about the study, so that the decision to prescribe nintedanib is clearly separated from the decision to include the patient in this active surveillance. The decision of treatment, including the intended duration of treatment, is at the discretion of the physician providing care for the patient.

Patients who have taken at least one dose of nintedanib will be included in the safety analysis.

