10. RESEARCH METHODS

10.1 STUDY DESIGN

200 IPF patients treated with nintedanib per the Indian label will be enrolled in this active surveillance program. They are classified into following groups:

- Group A. Patients who started treatment with nintedanib after 23rd January, 2017 and have permanently discontinued the drug (as decided by the investigator) at the time of participation in the active surveillance. Data for these patients will be collected in anonymized manner after getting approval from the Ethics Committees for data collection and sharing.
- Group B. Patients who started treatment with nintedanib after 23rd January, 2017 and are continuing the drug at the time of participation in the active surveillance.
- Group C. Patients who have been newly prescribed nintedanib at the time of participation in the active surveillance.

In addition 200 IPF patients treated with pirfenidone will also be enrolled. They are classified into following groups:

- Group I. Patients who started treatment with pirfenidone after the 23rd January, 2017 and have permanently discontinued the drug (as decided by the investigator) at the time of participation in the active surveillance. Data for these patients will be collected in anonymized manner after getting approval from the Ethics Committees for data collection and sharing.
- Group II. Patients who started treatment with pirfenidone after the 23rd January, 2017 and are continuing the drug at the time of participation in the active surveillance.
- Group III. Patients who have been newly prescribed pirfenidone at the time of participation in the active surveillance.

The medical records at the selected sites will be screened to enroll Group A and B patients in a retrospective manner. Group C patients will be enrolled prospectively. The first patient enrolled at a given site should be in the nintedanib group. Once a patient is enrolled into the nintedanib group, the site team is suggested to enrol the next eligible patient, who has initiated or will be initiating pirfenidone at the same site in the pirfenidone group.

The safety data for nintedanib treated patients will be collected for at least 52 weeks or till the discontinuation of the drug, whichever is earlier. Patients treated with pirfenidone will not be followed.

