At visit 1, the baseline characteristics (e.g. demographics, pulmonary function tests, HRCT evaluation etc., see [section 10.3.3](#)) will be recorded for all patients (either treated with nintedanib or pirfenidone).

The medical records of patients belonging to Group A and B will be evaluated to see if any ADRs and SAEs have occurred in the nintedanib treated arm during the duration of the treatment/ 52 weeks, whichever is earlier. Group B and Group C patients will be followed up according to clinical practice

for at least 52 weeks /discontinuation (whichever is earlier) from the start of the treatment at regular intervals (i.e. approximately every 4 weeks for the first 3 visits and approximately every 12 weeks thereafter till week 52). At each visit, all ADRs associated with nintedanib and SAEs will be recorded and reported per [section 12.2](#). In case a patient discontinues nintedanib before 52 weeks, all ADRs and SAEs will be collected till the date of discontinuation of nintedanib. There may be unscheduled visits between the scheduled visits. All ADRs and SAEs will also be collected at these unscheduled visits and entered into the eCRF. For nintedanib treated patients, certain information (e.g. co-medications, see [flowchart](#)) will also be collected at further and unscheduled visits (if available), as the status may change over time.

In case the patient is lost to follow up (patients not contactable for further visits), the site should attempt to contact the patient or patient's relative telephonically to gather the information on the vital status and record it in the eCRF.

Additionally, whenever the investigator becomes aware of SAEs and/or ADRs occurring in an enrolled patient before individual patient's end of study and it needs to be reported as per [section 12.2](#).

Patients who have taken at least one dose of nintedanib will be included in the safety analysis.

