10.5 SAMPLE SIZE

200 IPF patients treated with nintedanib according to approved Indian label (classified as Group A, B and C, see [section 10.1](#)) will be enrolled in this active surveillance program. The sample size of 200 is as per the request from the regulatory agency.

In addition 200 IPF patients who were treated with pirfenidone (classified as Group I, II and III, see [section 10.1](#)) at the same centres and during the same time frame will also be included. The baseline characteristic of these patients will be recorded at visit 1 and they will not be followed.

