10.7 DATA ANALYSIS

Analyses will be descriptive in nature including means, medians, standard deviation and interquartile range for continuous variables, and frequencies and percentages for binary and categorical variables with the corresponding 95% confidence intervals. For safety outcomes, incidence rates with corresponding 95% confidence intervals will be calculated. The baseline characteristics of 200 pirfenidone treated patients will be used to compare with the patients profile of the Nintedanib users. Whenever patient profiles differ between those treated with nintedanib and pirfenidone, cautious interpretation is required.

Subgroup analysis will be performed according to prior treatment (see [section 10.7.1](#)).

Any patient who meets the following criteria is treated as ineligible for safety analysis:

- Required registration procedure was not followed

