10.9 LIMITATIONS OF THE RESEARCH METHODS

The scientific objective of this active surveillance is to obtain an estimate of the occurrence of all ADRs and SAEs in IPF patients prescribed Nintedanib per the approved label in the real world setting. For retrospective data, there may be a possibility of missed information on adverse events. For patients followed prospectively, lost to follow up, loss of information and recall bias could impose limitations. Since only the cohort treated with Nintedanib will be followed up, it is impossible to assess the safety of Nintedanib compared to other drugs. The possible selection bias will be minimised by enrolling all patients who have initiated or will initiate nintedanib (Group A, B and C) from the date of commercial availability of drug (23rd January 2017) at selected centres and potential channelling bias will be assessed by recording the baseline characteristics of a comparator group of equal number of patients who have been treated with pirfenidone.

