10.10.1.1 Study approval, patient information, and informed consent

The review by Drug controller general of India (DCGI), Institutional Review Board (IRB) or Ethics Committee will be sought as per the institutional procedures before the start of this active surveillance program.

Prior to patient's participation in this active surveillance program, written informed consent must be obtained from each patient (or the patient's legally accepted representative) according to the regulatory and legal requirements of India (applicable for Group B/C and II/III patients). Each signature must be personally dated by each signatory and the informed consent and any additional patient-information form must be retained by the Investigator as part of the study records. A signed copy of the informed consent and any additional patient information must be given to each patient or the patient's legally accepted representative.

The Investigator must give a full explanation of this active surveillance program, regarding the collection of the safety data at specific time points to these participants. The Investigator obtains written consent of the patient's own free will with the informed consent form after confirming that the patient understands the contents. The Investigator must sign and date the informed consent form.

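### The SAP omits protocol Groups A and I and requires a signed consent form for every analysis set, yet declares no change from protocol 5.0

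*SAP*

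**What the plan says.** **Protocol 5.0.** Section 10.1 defines three nintedanib groups: A had permanently stopped the drug by participation, B is still taking it, and C is newly prescribed it. Pirfenidone Groups I, II and III mirror them.

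- Recruitment (10.1): "The medical records at the selected sites will be screened to enroll Group A and B patients in a retrospective manner".
- Route for Group A, with the same sentence for Group I (10.1): "Data for these patients will be collected in anonymized manner after getting approval from the Ethics Committees for data collection and sharing".
- Consent (10.10.1.1) follows the "legal requirements of India (applicable for Group B/C and II/III patients"; inclusion criterion 2 in 10.2.2.1 has the same limit.
- Sample size (10.5): "200 IPF patients treated with nintedanib according to approved Indian label (classified as Group A, B and C". Section 12.2 requires ADR and SAE collection for all three groups.
- Safety population (10.1): "Patients who have taken at least one dose of nintedanib will be included in the safety analysis". Section 10.7 adds "Any patient who meets the following criteria is treated as ineligible for safety analysis", and the one criterion listed is that the registration procedure was not followed.
- Bias (10.9): "The possible selection bias will be minimised by enrolling all patients who have initiated or will initiate nintedanib (Group A, B and C".

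**SAP.** Section 6.1 lists only Groups B, C, II and III, and says "The medical records at the selected sites will be screened to enroll Group B patients in a retrospective manner till the date of start" of participation. In 6.3 the Screened Set requires a signed ICF, the Entered Set lies within it, and the Treated Set lies within the Entered Set. All primary and secondary outcomes use the Treated Set, and baseline data use the Entered Set. In 6.2, violations A1.2 and A3.2 (no ICF, late ICF or no ICF date) exclude from all sets with no group limit. Sections 6.1 and 7.8 nevertheless repeat the protocol's one-dose rule. Section 4 states that nothing changed from protocol 5.0.

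**The concern.** The SAP does not implement the protocol version that it claims to follow. A signed form, which the protocol does not ask of Groups A and I, becomes the entry condition for every analysis. The SAP also contradicts itself, because the one-dose rule in 6.1 and 7.8 carries no consent condition while 6.3 does.

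The patients affected are not a random subset. Everyone in Group A has stopped the drug, and everyone in Group B was still on it at participation. Keeping B without A selects past starters for having stayed on treatment, and discontinuation due to adverse events is itself the secondary outcome.

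**Working it through.** **1. Set logic.** From SAP 6.3: Screened = ICF signed; Entered = Screened and eligible; Treated = Entered and at least one dose. Apply this to an eligible, dosed patient entered as the protocol allows:

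| Group | ICF required by protocol | Screened | Entered | Treated |
|---|---|---|---|---|
| A, no ICF | no | no | no | no |
| B | yes | yes | yes | yes |
| C | yes | yes | yes | yes |

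A Group I patient without an ICF likewise fails the Screened and Entered Sets. This is not a table artefact: the running text of SAP 6.1, 6.7 and 7.8.1 and items A1.3 and A3.3 name only Group B or II.

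**2. Direct loss if Group A patients were entered.** Let g be Group A's share of the 200 and D the share of the 200 who discontinue for any reason. Neither is in the documents. The Treated Set has 200(1 - g) patients and shows (D - g)/(1 - g). For g = 5, 10, 15 and 20% the set is 190, 180, 170 and 160. With D = 30% it shows 26.3, 22.2, 17.6 and 12.5%; for example, (0.30 - 0.10)/(1 - 0.10) = 22.2%.

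**3. Selection effect of Group B without Group A.** Assumptions: no deaths; past starts spread evenly over 555 days (23 January 2017 to 1 August 2018); adverse events stop treatment at 0.2 per year, or at 0.3 then 0.1, or at 0.6 then 0.15, changing at 3 months. Let S(t) be the probability of still being on drug at time t, T = 364/365.25 = 0.9966 years and W = 555/365.25 = 1.5195 years.

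- All starters (A+B, or C): 1 - S(T).
- Group B only: ∫₀ᵀ[S(u) - S(T)]du / ∫₀ᵂS(u)du. A past starter u years in is still on drug with probability S(u), and can stop within the 52 weeks only if u < T.
- Half B, half C: the mean of the two.

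At 0.2 per year, S(T) = exp(-0.1993) = 0.8193, so all starters show 18.1%. Group B shows [(1 - 0.8193)/0.2 - 0.9966 × 0.8193] / [(1 - 0.7379)/0.2] = 0.087/1.310 = 6.6%. The mean is 12.4%.

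| Stopping per year | All starters | B only | Half B | Loss, half B | Loss, quarter B | 95% CI half-width, n = 200 |
|---|---|---|---|---|---|---|
| 0.2 | 18.1% | 6.6% | 12.4% | 5.7 | 2.9 | 5.3 |
| 0.3 then 0.1 | 13.9% | 3.7% | 8.8% | 5.1 | 2.5 | 4.8 |
| 0.6 then 0.15 | 23.0% | 6.0% | 14.5% | 8.5 | 4.3 | 5.8 |

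Losses and half-widths are in percentage points; the half-width is 1.96√(p(1 - p)/200) at the all-starters value. The n = 200 comparison fits the case where no Group A patient was entered.

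Time on drug matters as much. If every Group B patient had been on drug for u at participation, the half-B loss is 0.5 × [S(T)/S(u) - S(T)]. That gives 0.7-1.9 points at 30 days, 2.1-6.1 at 90 days, 4.2-7.9 at 180 days and 6.9-11.5 at 52 weeks.

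**4. What bounds the Group B share.** Very little. SAP 3 puts 6 subjects under protocol version 2.0 and the rest under 5.0. At least 200 - 6 = 194 nintedanib patients therefore fall under criteria that admit past starters, but nothing says how many were past starters.

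**The case against.** **The SAP may have cost no patients.** A reader might infer that Group A data have been discarded. The documents do not support that. The rules exclude a Group A patient only if one was entered, and entered without an ICF. The SAP history table says that 6.1 follows protocol 5.0 and that the Screened and Treated Sets were updated by Group. That would fit a deliberate edit because nobody was entered, but no reason is given. SAP wording cannot recover patients who were never enrolled. This stands, and it limits the claim. It does not remove it, because Section 4 would still be wrong.

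**Fatal events and SAE rates.** A reader might also infer that these are understated. That needs patients who died on drug to count as Group A, and protocol 10.1 defines Group A by permanent discontinuation as decided by the investigator, without mentioning death. In a simulation of past starters (stopping 0.2 and death 0.23 per year, the latter ln 2/3 from the 3-year upper median survival in protocol 8), about 19% of all starters have a fatal event on drug. Group B shows 7.7%. Adding back only the Group A patients who did not die on drug gives 6.6%, so restoring Group A on that reading recovers nothing. With no deaths, and SAEs unrelated to stopping, the SAE rate does not change.

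**ADR rates.** Protocol 10.9 warns that retrospective records may miss adverse events, and Group A is wholly retrospective. The direction for ADR incidence is therefore uncertain.

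**The 10.9 control was never assured.** Enrolment stops at 200 with no A/B quota (10.2.2.2), so it is too strong to say that the SAP removed a working safeguard.

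**Existing provisions.** The one-dose rule does not repair the sets, because 6.3 assigns the outcomes to the Treated Set. Nor does the SAP 6.2 strategy for deviations: under the protocol, a Group A patient without an ICF is not a deviation. The consent date used in 6.6 is a minor matter. It affects only completely missing onset dates, and 7.8.1 sends missing dates to data management first.

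**Conclusion.** The contradiction is certain from the text and should be settled before database lock, because it defines the population for every primary and secondary outcome. Its numerical effect is not known.

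- If Group A patients were entered without an ICF, the Treated Set falls below 200 and the loss is selective.
- If none were entered, the SAP wording loses nobody. What remains is an undeclared departure and a 10.9 statement that does not hold as written.
- In either case, the percentage discontinuing due to adverse events is understated to the extent that Group B is present and eligible discontinuers are left out. On the assumed inputs the loss at half Group B is 5.1-8.5 points, close to or above the confidence-interval half-width. At a quarter it is 2.5-4.3 points, below that half-width. If all patients are Group C it is nil.

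The Group B share, time on drug and stopping rates are assumptions, so these figures illustrate the effect and do not estimate it. No claim is made on fatal events, SAE rates or the direction of ADR rates. Group I affects only the pirfenidone baseline comparison.

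**What to change.** Choose by what happened at the sites.

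**(a) Group A or I patients were, or still can be, entered.**
- Restore Group A in SAP 6.1, 6.7 and 7.8.1, and Group I in 6.1.
- Define the Screened Set as a signed ICF (B, C, II, III) or entry from anonymised records under Ethics Committee approval (A, I).
- Limit A1.2 and A3.2 to B/C and II/III, and align A1.3 and A3.3 with the protocol's groups.
- In 6.6, name a date that replaces the consent date for Group A.
- State whether patients who died on drug count as Group A.

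**(b) None were entered.** Declare the removal in SAP Section 4, correct the 10.9 statement in the report, and do not present results from B and C as incidence in all starters.

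Under both, state the number entered in each Group. Outcome tables by Group, at least B versus C, are optional but would show any difference. A count of eligible past starters found is also optional and may not exist, since protocol 10.2.3 requires a log only of included patients.

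**Cost.** Route (a) needs SAP wording and a revised set derivation. Collecting Group A records now would also need Ethics Committee approval and further record review. Route (b) needs one Section 4 entry and a stated limitation.

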## **6.2 IMPORTANT PROTOCOL VIOLATIONS**

The following table 6.2 defines the different categories of important protocol violations based on protocol versions 5.0. The final column (i.e. Excluded From) in both the tables describes which PVs will be used to exclude patients from the different patients analysis sets.

In this example, patients are either excluded from "All" analysis sets, "Treated Set" or "None" of the analysis sets. The PVs that will not exclude the patient from any analysis set are included for completeness and also to demonstrate a level of quality (or adherence to the protocol). of important PVs but not limited to:

Table 6.2: Important protocol violations

The following table defines the different categories

Category/ code	Description	Requirements	Detected by	Excluded From
A	Entrance criteria not met			
A1	Inclusion criteria not met for patients treated with nintedanib			
A1.1	Patients with documented diagnosis of IPF which is either not based upon ATS/ERS/JRS/ALAT 2011 guidelines (nintedanib naïve or pirfenidone pre-treated) or who have	Patients (nintedanib naïve or pirfenidone pre-treated) whose diagnosis of IPF is not as per the guideline	Manually	None

Category/ code	Description	Requirements	Detected by	Excluded From
	initiated or will initiate nintedanib not according to the package insert after the commercial availability of nintedanib in India (23rd January 2017).	ATS/ERS/JRS/AL AT 2011 and/or who have initiated or will initiate nintedanib not according to the package insert after the commercial availability of nintedanib in India (23rd January 2017).		
A1.2	Patients in whom it is not possible to obtain voluntary informed consent either from the patient or patient's legally authorised representative	Not provided ICF or ICF is provided too late or Missing ICF date.	Automated iPV- Programmatic	All
A1.3	Patients in whom data collection is not possible from the medical records applicable for Group B patients.	No data is collected from medical records or medical records are not available for the Group B patients	Manually	None
A1.4	Patients in whom information on baseline characteristics (which are required for registration procedure) mentioned in the protocol section 10.3.3 is not available.	Baseline characteristics data which is mandatory for the registration process (Section 10.3.3 from Protocol) is not available.	Manually	None
A2	Exclusion criteria met for patients treated with nintedanib			
A2.1	Patients who were previously treated with	Patients who have taken nintedanib	Manually	None

Category/ code	Description	Requirements	Detected by	Excluded From
	nintedanib.	before the commercial availability of drug in India (23rd January 2017).		
A2.2	Patients who have initiated or are planned to be concomitantly treated with pirfenidone	Patients who have initiated or are planned to be concomitantly treated with pirfenidone	Manually	None
A2.3	Patients who are participating in a clinical trial	Patients who are participating in a clinical trial	Manually	None
A3	Inclusion criteria not met for patients treated with pirfenidone			
A3.1	Patients with documented diagnosis of IPF which is either not based upon ATS/ERS/JRS/ALAT 2011 guidelines (antifibrotic naïve) or who have initiated or will initiate pirfenidone not according to the package insert after the commercial availability of nintedanib in India (23rd January 2017).	Patients (antifibrotic naïve) whose diagnosis of IPF is not as per the guideline ATS/ERS/JRS/ALAT 2011 and/or who have initiated or will initiate pirfenidone not according to the package insert after the commercial availability of nintedanib in India (23rd January 2017).	Manually	None
A3.2	Patients in whom it is not possible to obtain voluntary informed consent either from the patient or patient's	Not provided ICF or ICF is provided too late or Missing ICF date.	Automated iPV- Programmatically	All

Category/ code	Description	Requirements	Detected by	Excluded From
	legally authorised representative.			
A3.3	Patients in whom data collection is not possible from the medical records applicable for Group II patients.	No data is collected from medical records or medical records are not available for Group II patients.	Manually	None
A3.4	Patients in whom information on baseline characteristics (which are required for registration procedure) mentioned in the protocol section 10.3.3 is not available.	Baseline characteristics data which is mandatory for the registration process (section 10.3.3 from Protocol) is not available.	Manually	None
A4	Exclusion criteria met for patients treated with pirfenidone			
A4.1	Patients who were previously treated with nintedanib or pirfenidone.	Patients who have treated with nintedanib or pirfenidone before the commercial availability of drug in India (23rd January 2017).	Manually	None
A4.2	Patients who have initiated or will initiate pirfenidone concomitantly with nintedanib.	Patients who have initiated or will initiate pirfenidone concomitantly with nintedanib.	Manually	None
A4.3	Patients who are participating in a clinical trial.	Patients who are participating in a clinical trial.	Manually	None

**KEY:** IPV- Important Protocol Violation

**Note:** Automated PVs are those detected via an automated programming process. Manual PVs are those that cannot be detected through the data stored in the trial database and is picked up through other processes such as site monitoring or IPV that is too complex to program which identified by the trial team.

Important protocol violations will be defined and documented prior to clinical database lock. A strategy for dealing with data affected by protocol deviations will be agreed upon by the coordinator, sponsor and biostatistician before clinical database lock.

